7.3 Randomization

Once all screening procedures are complete and all eligibility criteria have been met, the subject may be randomized into the study by calling IVR/IWR system. Before randomizing a subject, site staff should prospectively assess scheduling conflicts with the subject for the study from screening through EOTP.

Randomization may occur on the same day as the first dose of IP (ie, study day 1) or it may occur up to 4 days prior to the first dose of IP. Adverse events will be reported beginning from the date of randomization.

7.4 Study Day 1/Week 1

Study day 1 (ie, week 1) is the first day IP (darbepoetin alfa or placebo) is administered.

The day 1 / week 1 study procedures (eg, ECOG, laboratory sample draws) may be performed up to 1 day prior to IP dosing.

The following assessments and procedures will be completed on study day 1 (week 1):

- Vital signs and weight
- The presence of a central or mid-line venous catheter
- ECOG performance status
- Assess for signs and symptoms of clinically relevant TVE. If present, perform appropriate laboratory, diagnostic, and medical imaging for suspected TVE
- Darbepoetin alfa antibody collection
- Endogenous EPO level
- Adverse events
- Concomitant medications, radiotherapy, anti-cancer therapy, anti-cancer surgery, and RBC transfusions
- Central laboratory tests: clinical chemistries and CBC with differential (including hemoglobin for statistical analyses), **CRP**, and soluble transferrin receptor
- Local laboratory hemoglobin for dosing determination
- Access IVR/IWR system for medication assignment
- Subcutaneous administration of IP

7.5 Treatment Period (Q3W Visits)

Study visits will occur every 3 weeks \pm 6 days with subcutaneous IP administration Q3W during the treatment period. IP will be discontinued within 3 weeks after the last dose of chemotherapy, or upon the determination of disease progression, whichever occurs first.

For all study visits during the treatment period, study procedures (eg, ECOG, laboratory sample draws) may be performed up to 1 day prior to IP dosing.

The following assessments and procedures will be performed during the treatment period:

- Vital signs and weight
- · The presence of a central or mid-line venous catheter
- ECOG performance status
- Assessment of disease progression
- Assess for signs and symptoms of clinically relevant TVE. If present, perform appropriate laboratory, diagnostic, and medical imaging for suspected TVE
- Imaging studies Q9W (or earlier if clinically indicated) until documented disease progression (see Section 7.1.6)
- Central laboratory tests: clinical chemistries and CBC with differential (including hemoglobin for statistical analyses), Tsat, ferritin, iron, and TIBC. Central laboratory tests will continue until the next Q3W study visit that occurs after the last dose of IP
- Local laboratory hemoglobin for IP dosing determination. Local laboratory hemoglobin testing will continue until the next Q3W study visit that occurs after the last dose of IP
- Access IVR/IWR system for medication assignment or to register a subject's discontinuation from IP (if applicable)
- Subcutaneous Q3W administration of IP
- Subjects who discontinued IP but have not had disease progression will continue Q3W visits and Q9W imaging studies until disease progression has been determined. Subjects who are unable to continue Q3W visits and Q9W imaging studies until disease progression should complete EOTP procedures at no later than their next Q3W visit and will be asked to enter the LTFU period

Concomitant medications, radiotherapy, anti-cancer therapy, anti-cancer surgery, and RBC transfusion information will be collected throughout the treatment period. AEs and SAEs will be collected up to 30 days after the last dose of IP.

7.6 End of Treatment Period

Subjects will complete the EOTP visit at the next Q3W visit (± 6 days) after disease progression has been determined either by imaging studies or by clinical assessments in the absence of imaging confirmation. Subjects who are unable to continue Q3W visits and Q9W imaging studies until disease progression should complete EOTP procedures

at no later than their next Q3W visit (\pm 6 days). At the time of the EOTP visit, any subject who has experienced a serious and treatment related adverse event during the study, as determined by the investigator, will continue to be followed for that event, until the event is resolved or considered stable; all EOTP visit procedures may still be conducted prior to resolution.

The following EOTP assessments and procedures will be required for all subjects:

- Vital signs and weight
- The presence of a central or mid-line venous catheter
- ECOG performance status
- Assess for signs and symptoms of clinically relevant TVE. If present, perform appropriate laboratory, diagnostic, and medical imaging for suspected TVE
- Adverse events, concomitant medications, radiotherapy, anti-cancer therapy, anticancer surgery, and RBC transfusions
- Central laboratory serum chemistries and CBC with differential (including hemoglobin for statistical analyses) (except if EOTP visit occurs following the Q3W visit after the last dose of IP)
- Local laboratory hemoglobin (except if EOTP visit occurs following the Q3W visit after the last dose of IP)
- Darbepoetin alfa antibody

7.7 Long-term Follow-up Period

After the EOTP visit, subjects will enter the LTFU period and will visit the clinic at 3⁻month intervals (± 2 weeks). For subjects who are unable to come to the clinic, site staff should contact the subjects by phone to ascertain survival status.

The following data will be collected by the investigator or site personnel and forwarded to Amgen or designee:

- Overall survival status
- ESA administration (eg, date of administration, type, and dose)
- Anti-cancer therapy (eg, date of administration, type and dose)
- Anti-cancer surgery
- Radiotherapy

7.8 End of Study

The EOS for a subject is when the subject has died or when approximately 2700 deaths have occurred. For any subjects still receiving IP when the 2700th death occurs, these subjects may continue to receive IP per protocol.

7.9	Tumor Sample for Future Biomarker Evaluation (Optional)
CCI	
i 🚃	
-	

CCI

Tumor Sample Storage and Destruction

8. REMOVAL AND REPLACEMENT OF SUBJECTS

8.1 Removal of Subjects

Subjects have the right to withdraw fully or partially from the study at any time and for any reason without prejudice to his or her future medical care by the physician or at the institution.

Withdrawal of full consent for a study means that the subject does not wish to receive further investigational treatment and does not wish to or is unable to continue further study participation. Any subject may withdraw full consent to participate in the study at any time during the study. The investigator will discuss with the subject the most appropriate way to withdraw to ensure the subject's health.

Withdrawal of partial consent means that the subject does not wish to take IP any longer but is still willing to collaborate in providing further data by continuing on study (eg, participate in all subsequent imaging visits until disease progression and/or to be followed during the LTFU period). Withdrawal of partial consent also means that the subject, although having completed IP or stopped receiving IP for other reasons, is still willing to collaborate in providing further data by continuing on study (eg, participate in all subsequent imaging visits until disease progression and/or to be followed during the LTFU period).

Reasons for discontinuation of IP or study visits or procedures might include:

- withdrawal of full consent
- withdrawal of partial consent
- administrative decision by the investigator or Amgen
- pregnancy (report on Pregnancy Notification Worksheet, see Appendix F)
- ineligibility
- lost to follow up
- significant protocol deviation
- subject non-compliance
- adverse event

8.2 Replacement of Subjects

Subjects who prematurely discontinue following randomization will not be replaced.

9. SAFETY DATA COLLECTION, RECORDING, AND REPORTING

9.1 Adverse Events

9.1.1 Definition of Adverse Event

An adverse event is defined as any untoward medical occurrence in a clinical investigation subject occurring from the time that the subject has signed informed consent through 30 days after last dose of IP and does not necessarily have a causal relationship with study treatment. The investigator is responsible for ensuring that any adverse events observed by the investigator or reported by the subject are recorded in the subject's medical record. These records are the source documents from which data are extracted and reported to Amgen per the reporting procedures (Section 9.1.2).

The definition of adverse event includes worsening of a pre-existing medical condition. Worsening indicates the pre-existing medical condition (eg, cancer, diabetes, migraine headache, gout) has increased in severity, frequency, and/or duration, and/or has an association with a significantly worse outcome. A pre-existing condition that has not worsened during the study, but involves an intervention such as elective cosmetic surgery or a routine standard of care medical procedure while on study, is not considered an adverse event.

Disease progression (ie, progression of cancer) will not be considered an adverse event, nor a serious adverse event if International Conference for Harmonization (ICH) criteria for seriousness are met. Disease progression will instead be documented on a specific case report form and analyzed separately as a key secondary study endpoint. Similarly,

disease progression as a cause of death will be captured on a Death Summary case report form.

There are several well documented adverse events in oncology subjects that are known to occur during chemotherapy treatment such as nausea, vomiting, diarrhea, constipation, anorexia, and fatigue. These symptoms should not be considered adverse events, unless:

- Severity, frequency, or duration of the symptom(s) has increased from baseline
- Symptom(s) meets a serious criterion (report as AE and SAE)
- Symptom(s) is considered possibly related to investigational product

The investigator is responsible for reviewing laboratory test results and determining whether an abnormal value in an individual study subject represents a change from the subject's baseline values. In general, an abnormal laboratory finding without clinical significance (based on the investigator's judgment) should not be considered adverse events. However, a laboratory value change that requires treatment or adjustment in current therapy would be considered an adverse event. Where applicable, clinical sequelae, and not the laboratory abnormality, should be considered an adverse event.

9.1.2 Reporting Procedures for Adverse Events

All adverse events occurring after randomization through 30 days after last dose of IP as recorded in the subject's medical record, will be reported to Amgen via the Adverse Event Summary CRF. TVEs, and adverse events associated with RBC transfusions administered during the treatment period, that occur through the EOTP or 30 days after the last dose of IP, whichever occurs later, also will be documented in the CRF. VTEs are captured on a specific CRF page.

The investigator must assign the following adverse event attributes:

- Adverse event diagnosis or syndrome(s), if known (if not known, signs or symptoms)
- Event description (with detail appropriate to the event)
- Dates of onset and resolution
- Severity
- Assessment of relatedness to IP
- · Assessment of relatedness to transfusion
- Assessment of relatedness to chemotherapy
- Action taken

The adverse event severity grading scale used will be the CTCAE. The severity grading scale used in this study is described in Appendix B.

The investigator must assess whether the adverse event is possibly related to the IP. This relationship is indicated by a "yes" or "no" response to the question: "Is there a reasonable possibility that the event may have been caused by the IP?"

The investigator must assess whether the adverse event is possibly related to transfusion. This relationship is indicated by a "yes" or "no" response to the question: "Is there a reasonable possibility that the event may have been caused by RBC transfusion?"

The investigator must assess whether the adverse event is possibly related to chemotherapy. This relationship is indicated by a "yes" or "no" response to the question: "Is there a reasonable possibility that the event may have been caused by chemotherapy?"

Medically significant adverse events considered related to the IP by the investigator will be followed until resolved or considered stable.

The investigator's clinical judgment will be used to determine whether a subject should be removed from treatment or from the study due to an adverse event. A subject may also voluntarily withdraw from treatment due to an adverse event. If the subject is withdrawn, the subject should be strongly encouraged to undergo at a minimum an end-of-treatment assessment. The subject should be followed until symptoms cease or the condition becomes stable.

9.2 Serious Adverse Events

9.2.1 Definition of Serious Adverse Event

A serious adverse event (SAE) is an adverse event that meets at least one of the following serious criteria:

- fatal
- life threatening (places the subject at immediate risk of death)
- requires in-patient hospitalization or prolongation of existing hospitalization
- results in persistent or significant disability/incapacity
- congenital anomaly/birth defect, and/or
- other significant medical hazard

The investigator is responsible for ensuring, for all subjects who have signed an informed consent, that all serious adverse events occurring from signing of informed consent (inclusive of the screening phase) through 30 days after last dose of IP are recorded in the subject's medical record. This includes serious adverse events

observed by the investigator or reported by the subject. These records are the source documents from which data are extracted and reported to Amgen per the reporting procedures (Section 9.2.2).

An adverse event meets the serious criterion of "requires hospitalization", if the event necessitates an admission that includes a minimum of an overnight stay in a health care facility.

If an investigator considers an event to be clinically important, but it does not meet any other serious criteria, the event could be reported under the criterion of "other significant medical hazard". Examples of such events include allergic bronchospasm, convulsions, and blood dyscrasias, which result in an emergency room visit, outpatient surgery, or other urgent intervention.

If the following interventions are performed as standard of care and not associated with a new health issue or worsening of a pre-existing health issue, the health issue for which the intervention is performed will not be considered an adverse event, nor a serious adverse event.

- Insertion of a central line as an outpatient or associated with hospitalization
- Blood transfusion(s)
- Hospitalization for the purpose of chemotherapy administration

If there is a health complication as a result of the intervention, the complication would be reported as an adverse event; if the complication meets at least 1 serious criterion, the complication would be also reported as a serious adverse event.

9.2.2 Reporting Procedures for Serious Adverse Events

The Investigator is responsible for ensuring that all serious adverse events observed by the Investigator or reported by the subject that occur after signing of informed consent through 30 days after last dose of IP as recorded in the subject's medical record and are submitted to Amgen. Serious TVEs, and SAEs associated with RBC transfusions administered during the treatment period, that occur through the EOTP or 30 days after the last dose of IP, whichever occurs later, also will be reported to Amgen. During long-term follow-up period, SAEs will not be reported to Amgen, except for SAEs occurring after 30 days post last dose of IP AND thought to be possibly related to IP. These events are to be submitted to Amgen.

The serious adverse event must be submitted to Amgen within 24 hours following the Investigator's knowledge of the event via the applicable CRF. If the electronic

data capture (EDC) system is unavailable to the site staff to report the Serious Adverse Event, the information is to be reported to Amgen via a Serious Adverse Event (SAE) Contingency Reporting Form within 24 hours of the Investigator's knowledge of the event. See Appendix C for a sample of the Serious Adverse Event Contingency Reporting Form. If the first notification of a Serious Adverse Event is reported to Amgen via the Serious Adverse Event Contingency Reporting Form, the data must be entered into the EDC system when the system is again available.

New information relating to a previously reported serious adverse event must be submitted to Amgen. All new information for serious adverse events must be sent to Amgen within 24 hours following knowledge of the new information. The Investigator may be asked to provide additional follow-up information, which may include a discharge summary or extracts from the medical record; autopsy reports should be provided for deaths, if available. Information provided about the serious adverse event must be consistent with that recorded on the applicable CRF (eg, Adverse Event Summary CRF). If a subject is permanently withdrawn from the study because of a serious adverse event, this information must be submitted to Amgen.

The investigator should notify the appropriate IRB, ethics committee, or head of the medical institution, when applicable, of serious adverse events occurring at the site and other adverse event reports received from Amgen, in accordance with local procedures and statutes.

To comply with **worldwide** reporting regulations for serious adverse events, the treatment assignment of subjects who develop serious, unexpected, and related adverse events may be unblinded by Amgen **before submission to regulatory authorities**. **Investigators will receive notification of related serious adverse events reports sent to regulatory authorities in accordance with local requirements.**

Amgen will report serious adverse events and/or suspected unexpected serious adverse reactions as required to regulatory authorities, investigators/institutions, and IRBs/IECs in compliance with all reporting requirements according to local regulations and good clinical practice.

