EpoR	Erythropoietin receptor
ESA	Erythropoiesis stimulating agent
FDA	Food and Drug Administration
FDG-PET	Fluorodeoxyglucose-PET
g/dL	Gram per deciliter
GBG	German Breast Group
GGT	Gamma-glutamyltransferase
GOG	Gynecologic Oncology Group
HIV	Human immunodeficiency virus
HR	Hazard ratio
HSA-free	Human serum albumin-free
ICF	Informed consent form
ICH GCP	International Conference on Harmonisation Tripartite Guideline on Good Clinical Practice
ID	Identification
IEC/IRB	Independent ethics committee/institutional review board
IP	Investigational product
IV	Intravenous
IVR/IWR System	Interactive Voice Response/Interactive Web Response System
PPD	
kg	Kilogram
LDH	Lactate dehydrogenase
LTFU	Long-term follow-up
MCH	Mean corpuscular hemoglobin
MCHC	Mean corpuscular hemoglobin concentration
MCV	Mean corpuscular volume
MDS	Myelodysplastic syndromes
mL	Milliliter
MRI	Magnetic resonance imaging

Abbreviation or Term	Definition/Explanation
NA	Not applicable
NE	Inevaluable
ng	Nanogram
NSCLC	Non-small cell lung cancer
ODAC	Oncologic Drug Advisory Committee
OR	Odds ratio
OS	Overall survival
PD	Progressive disease
PE	Physical examination or pulmonary embolism
PET	Positron emission tomography
PET-CT	Positron emission tomography-computer tomography
PFS	Progression-free survival
pg	Picogram
PICC	Peripherally-inserted central catheter
PIN	Personal identification number
PR	Partial response
Q3M	Once-every-3-months
Q3W	Once-every-3-weeks
Q9W	Once-every-9-weeks
QW	Once-weekly
RBC	Red blood cell
RECIST	Response evaluation criteria in solid tumors
rHuEPO	Recombinant human erythropoietin
SAE	Serious adverse events
SAER	Serious adverse event report
SCLC	Small cell lung cancer
Screening hemoglobin	Local laboratory hemoglobin; sample obtained within 7 days prior to randomization
Screening period	Starts when the subject signs and dates the informed consent form and ends when the subject is randomized or screen failed. Must not exceed 21 days.
SD	Stable disease
SUSAR	Suspected unexpected serious adverse reactions
TIA	Transient ischemic attack
TIBC	Total iron binding capacity
Tsat	Transferrin saturation

Abbreviation or Term	Definition/Explanation
Treatment period	Starts when the subject is randomized and ends at the next Q3W visit after disease progression has been determined (EOTP). Note that EOTP is based on disease progression, not IP dosing.
TVE	Thrombovascular event
μg	microgram
ULN	Upper limit of normal
US	Ultrasound
VTE	Venous thromboembolic event
WBC	White blood cell
Wk	Week

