7.1.10 Adverse Events Reporting

Adverse events starting at randomization through 30 days after last dose of IP will be reported to Amgen. All serious adverse events (SAEs) occurring from the date the subject signs the ICF through 30 days after the last dose of IP will be reported to Amgen. All TVEs, and adverse events associated with RBC transfusions administered during the treatment period, will be reported through the EOTP or 30 days after the last dose of IP, whichever occurs later. Refer to Section 9 for more detail on adverse events reporting.

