Appendix A. Schedule of Assessments

- a. The screening period, which starts when the subject signs and dates the ICF and ends when the subject is randomized or screen failed, must not exceed 21 days. The local laboratory hemoglobin sample to confirm the eligibility hemoglobin value ≤ 11.0 g/dL must be obtained within 7 days prior to randomization. If the pre-chemotherapy baseline scan was performed more than 28 days prior to randomization, an additional scan must be performed and reviewed by the investigator to confirm that the patient has not progressed before randomization.
- b. Vital signs include temperature and resting BP (systolic and diastolic). Weight, presence of new / replaced central or mid-line venous catheters, and radiotherapy information will be collected during screening and during the treatment period. Anti-cancer therapy and anti-cancer surgery information will be collected during the treatment period.
- c. All SAEs that occur after the subject signed the ICF through 30 days post last dose of IP will be collected. All AEs will be collected after randomization until 30 days post last dose of IP. Signs and symptoms of clinically relevant TVEs will be assessed at each visit during the treatment period. If present, appropriate labs, diagnostic, and imaging will be performed. All TVEs, and adverse events associated with RBC transfusions occurring during the treatment period, will be documented in the CRF through the EOTP or until 30 days after the last dose of IP, whichever occurs later.
- d. IP will be administered SC Q3W during the treatment period. IP will be discontinued within 3 weeks after the last dose of chemotherapy, or upon the determination of disease progression, whichever occurs first. Subjects who discontinued IP but have not had disease progression will continue Q3W visits and Q9W imaging studies until progression has been determined. Subjects who are unable to continue Q3W visits and Q9W imaging studies until disease progression should complete EOTP procedures at their next Q3W visit and will be asked to enter the LTFU period.
- e. Central lab clinical chemistries includes creatinine, bilirubin, ALT, AST. CRP will be performed at Day 1 only.
- f. Central lab CBC includes WBC with differential, hemoglobin, hematocrit, platelet count.

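### Section 9.2.2 sets no explicit duty to report a possibly related SAE, other than a serious TVE or a transfusion-associated SAE, that arises between 30 days after the last dose and EOTP

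*Protocol*

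**What the plan says.** Protocol Section 9.2.2 contains three reporting rules for SAEs.

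- **General rule.** The investigator submits all SAEs "that occur after signing of informed consent through 30 days after last dose of IP".
- **Extended rule.** "Serious TVEs, and SAEs associated with RBC transfusions administered during the treatment period, that occur through the EOTP" or through 30 days after the last dose, whichever is later, are also reported.
- **Late related-SAE rule.** "During long-term follow-up period, SAEs will not be reported to Amgen, except for SAEs occurring after 30 days post last dose of IP" that are also thought possibly related to IP. The next sentence says that these are to be submitted.

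The periods are defined elsewhere. Section 7.7 states: "After the EOTP visit, subjects will enter the LTFU period". The Study Glossary adds: "Note that EOTP is based on disease progression, not IP dosing". Section 7.5 keeps subjects who are off drug in the treatment period: "Subjects who discontinued IP but have not had disease progression will continue Q3W visits and Q9W imaging studies until disease progression has been determined".

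Section 7.1.10 sets the 30-day limit on SAE reporting to the sponsor ("All serious adverse events (SAEs) occurring from the date the subject signs the ICF through 30 days after the last dose of IP will be" …) and the TVE and transfusion extension, then refers the reader to Section 9. Appendix A footnote c does the same without the cross-reference: "All SAEs that occur after the subject signed the ICF through 30 days post last dose of IP will be collected". Neither mentions late related SAEs.

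**The concern.** The general rule ends at a point set by dosing. The late related-SAE rule starts at a point set by progression. IP stops within 3 weeks after the last chemotherapy dose or at progression, whichever is first, so a subject who completes chemotherapy without progressing reaches the first point before the second. In between, the text requires only serious TVEs and transfusion-associated SAEs to be sent to the sponsor.

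The same related event would have to be reported before the interval and again after it. Subjects are still seen every 3 weeks during the interval, and the protocol keeps TVE reporting open there, so it recognises a need for surveillance. The SAP's events-of-interest table (Section 5) includes antibody-mediated pure red cell aplasia (PRCA), convulsions, severe cutaneous reactions and hypersensitivity, none of which the extended rule covers as such. The only post-baseline antibody sample is at EOTP, so an antibody-mediated event could first show itself inside the interval. What is at stake is expedited safety reporting: the sponsor cannot pass on what sites are not told to send.

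**Working it through.** No figure in the plan is in dispute, so the check sets the rules beside the period definitions and then counts days.

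**Coverage.** Let D be the day of the last IP dose and E the day of the EOTP visit.

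| Rule | Events covered | Applies |
|---|---|---|
| General | all SAEs | consent to D + 30 |
| Extended | serious TVEs, transfusion-associated SAEs | to the later of E and D + 30 |
| Late related | SAEs possibly related to IP | LTFU, that is, after E |

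Where E is later than D + 30, a possibly related SAE of any other kind with onset between the two is in no row.

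**Whether another section closes it.** The 30-day limit is repeated in Section 7.5 (collection), 9.1.1 (adverse event definition), 9.2.1 (recording of SAEs), 7.1.10 and Appendix A footnote c. None carries a late related-SAE exception. Section 7.6 lists adverse events among the EOTP assessments and requires continued follow-up of serious treatment-related events, but neither provision is a duty to report a new late event.

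**Length.** Gap = E − (D + 30) when positive, otherwise none. E is the next three-weekly visit after progression is determined. On time, dose n falls on day 1 + 21(n − 1), and week w starts on day 1 + 7(w − 1). Dose 6 is then day 1 + 21 × 5 = 106, as in the visit table of SAP Appendix A, and its window closes on day 106 + 30 = 136. Week 28 is day 1 + 7 × 27 = 190.

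| Case | E | Gap |
|---|---|---|
| Progression determined before the first visit after D | D + 21 (D + 15 to D + 27 with the ±6-day window) | none |
| Progression determined at that visit | D + 42 (D + 36 to D + 48) | 42 − 30 = 12 days (6 to 18) |
| Progression first seen on a scan 9 weeks after D (assumed) | D + 63 + 21 = D + 84 | 84 − 30 = 54 days |
| Six doses, week 28 scan | 190 + 21 = day 211 | 211 − 136 = 75 days |
| Six doses, week 37 scan | 253 + 21 = day 274 | 274 − 136 = 138 days |
| Six doses, week 46 scan | 316 + 21 = day 337 | 337 − 136 = 201 days |

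The week 28 case takes progression as determined on the visit day. If it were determined a few days earlier, EOTP would be the week 28 visit itself and the gap 190 − 136 = 54 days.

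The first case shows the opposite fault. EOTP falls before D + 30, so the instruction not to report in LTFU overlaps the general rule that requires reporting.

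**The case against.** The strongest reply is that the text is ambiguous rather than exclusionary. The exception is triggered by the 30-day mark and relatedness, the events are then said to be for submission, and the only instruction not to report is addressed to LTFU. A site could reasonably treat 30 days as the boundary and send every later related SAE. This stands in part: nothing tells a site to withhold such an event. But the exception sits inside a sentence confined to LTFU, and the words that follow refer back to it, so the text creates no duty before EOTP.

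A reader might infer three stronger things that the documents do not support.

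- **That no SAE in the interval is reportable.** Serious TVEs and transfusion-associated SAEs are reportable through EOTP, and Section 2.2 describes thromboembolic risk as well documented for this drug class.
- **That related events would be lost.** Adverse events are an EOTP assessment, serious treatment-related events are followed to resolution or stability (Section 7.6), and date and primary cause of death are collected throughout (Section 7.1.11). These do not replace expedited reporting, but they make disappearance unlikely.
- **That the amendment log proves a drafting slip.** It shows a late related-SAE sentence without the LTFU limit, but that is superseded text and no evidence of error.

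It is also fair that Section 7.1.10 defers to Section 9 and so need not repeat each exception; aligning it is tidying. Finally, the day counts measure calendar time, not events. Six doses and the scan weeks are chosen examples: eligibility requires only 2 further expected cycles, and IP may continue with myelosuppressive maintenance. Subjects who cannot continue visits complete EOTP by their next three-weekly visit, which can shorten or remove the interval.

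**Conclusion.** The point holds for a defined residue: SAEs possibly related to IP that are neither serious TVEs nor transfusion-associated, with onset after last dose + 30 days and before EOTP, in subjects who stop IP without progression. For these the protocol states no reporting requirement, although it requires the same event to be submitted on either side of the interval.

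The interval is about 12 days (6 to 18) when progression is found at the first three-weekly visit after the last dose, and 75 days in the six-dose, week 28 illustration. It lengthens with later progression and vanishes if progression comes before the next visit. Those figures assume on-time doses and visits, except where a range is shown. The documents give no rate for such events, so the number of affected reports cannot be estimated. It would be wrong to conclude that every subject who finishes chemotherapy without progressing has an unreported event; such a subject is only exposed to the gap if still progression-free at the next visit.

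This is a defect of scope in one safety-reporting sentence. Sample size, power, significance level and the analyses of OS, PFS and transfusion are unaffected.

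**What to change.** Reword the third rule in Section 9.2.2 so that it is anchored to dosing alone. Beyond 30 days after the last dose of IP, before or after EOTP, any SAE thought possibly related to IP is submitted; other SAEs are not, apart from the serious TVEs and transfusion-associated SAEs already covered. The 24-hour deadline in the following paragraph can stay as it is. Add the same exception, or a pointer to it, in Section 7.1.10 and Appendix A footnote c. Anchoring to dosing also removes the overlap when EOTP falls within 30 days of the last dose.

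The cost is one amended sentence with two alignments, and probably a few additional SAE reports from visits that already take place.

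The SAP (Section 9.2) records that dosing ended on 8 May 2017 and data collection on 7 June 2017, so an amendment may no longer be practical. In that case, check the records for possibly related SAEs with onset between last dose + 30 days and EOTP that were not sent to the sponsor, and state the limitation in the clinical study report. A last dose on 8 May 2017 has its 30-day window closing on 7 June 2017, so the check concerns subjects whose last dose was earlier.
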